Aim 2: Test the effects of the *Baa nnilah* intervention versus usual care using a wait-list control group effectiveness trial among 200 randomly assigned AI men and women 25 and older who have CI on the Apsáalooke Reservation.

Primary hypothesis: Those AI adults on the Apsáalooke Reservation participating in the *Baa nnilah* intervention will have significant improvement in quality of life using the SF-12 measure compared to a wait-listed control group immediately following the intervention and at 6 and 12 months post-intervention.

[figure not shown]
Secondary hypothesis: Those AI adults on the Apsáalooke Reservation participating in the *Baa nnilah* intervention will have significant improvement in measures of satisfaction in and participation with social roles and activities, social isolation, patient activation, health care relationship, physical function, and depression compared to a wait-listed control group immediately following the intervention and at 6 and 12-months post-intervention. Our mixed-methods design includes a qualitative evaluation of fidelity and acceptability immediately post-intervention.

This study is considered a Phase 3 clinical trial. Please see the attached document, "Protection of Human Subjects" from our grant application that contains human subjects information (some overlap with what is below) and our Data Safety and Monitoring Plan, which is required for Phase 3 clinical trials. This clinical trial has been registered at Clinicaltrials.gov with the following NCT identifier: NCT03036189.

As this project takes place on a reservation, please see the attached letter of support/approval from the Crow Nation.

See picture below for a graphic depiction of our study design:

Research Design of the *Báa nnííłah* Program A Group Randomized Trial

B. RESEARCH PROCEDURES INVOLVED. Provide a short description of sequence and methods of procedures that will be performed with human subjects. Include details of painful or uncomfortable procedures, frequency of procedures, time involved, names of psychological tests, questionnaires, restrictions on usual life patterns, and follow up procedures

There are three different groups from whom data will be gathered. Answers to the questions below are grouped according to who is providing the information.

1. Participants of intervention: all participants
2. Participants of intervention: subgroup
3. Intervention facilitators

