1. Participants of intervention: all participants: 200 Crow community members will be recruited by other community members (described below under D5), provide informed consent (form attached), and be randomly assigned by family/friend cluster to an intervention or wait-list control group (both groups will receive the intervention). Random assignment will occur via cluster so that family members or friends who are interested in participating in the intervention together will remain in the same group. During the month of October 2017, groups of approximately 10 community members will attend an orientation and data collection session – this is the baseline data collection. The groups are based on the community in which they will attend the intervention meetings and include: Wyola, Lodge Grass, Crow Agency, Hardin, and Pryor, MT.

[figure not shown]
During the orientation/data collection session, participants will complete a survey and 3 exercises. All measures in the survey that are in an index form (one measure with multiple questions) come from the NIH PROMIS measure bank (<http://www.healthmeasures.net/index.php>), are other validated measures, or are demographic or fidelity measures used in other studies. All measures

are included with the application and begin with the page labeled "Measures". The survey responses and results of the exercises will be on a tablet computer and will look similar on the computers (the measures attached are in different formats at present).

[figure not shown]
The survey questions will be read out loud by a project staff member. Participants will be seated so that they do not see the responses being entered into other computer tablets by other participants. We are working with the MSU HELPS lab to facilitate data collection. Survey respondents will provide their responses on tablet computers using Qualtrics offline software and unique identification codes. Once a respondent has submitted the survey, those answers will not be viewable by subsequent research participants. The responses will upload to the secure Qualtrics servers once the tablets are again connected to a wi-fi network. Data will not be maintained on the tablet computers in the long term.

Three basic physical function tests will be performed: timed up and go (TUG), static balance assessment (BESS), and 6 minute walk. Brief descriptions of the tests are below. Responses will be entered into the computer tablets.

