The Bighorn Valley Health Center (BVHC), a Federally Qualified Health Center located in Hardin, Montana, represents the primary site where the research will be performed.

Recruitment and study orientation: Intervention mentors (*Aakbaabaaniilea*) will take the lead in participant recruitment, using the strength of *Iishamaaalaxxia*, the Apsáalooke clan system, of which everyone is a part. The *Aakbaabaaniilea* will meet as a group with [name] and bring to the meeting a list of potential participants of the same gender, in keeping with respectful kinship relationships. Since the community is very close knit, *Aakbaabaaniilea* will know who has or does not have a CI. Use of *Iishamaaalaxxia* and care in *Aakbaabaaniilea* selection will ensure that there will not be overlap among the list of potential participants. The meeting between the *Aakbaabaaniilea* and [name] will cover participant recruitment, which includes contacting potential participants to explain the study and asking if they wish to be involved in the project. The *Aakbaabaaniilea* will be trained to randomly assign participants to the intervention group or wait-list group using a permuted block randomization protocol with 10 groups in each condition and 10 participants per group. The 10 groups (per condition) will be conducted at the same time, for a 4-month period to allow for 7 meetings approximately every two weeks (See Tables 5 and 8 of the Research Strategy section).

Aakbaabaaniilea will keep a log of refusals and reasons for refusing, and will recruit until they have 10 participants (each) in the intervention and wait-list group. Building the groups in this manner is also appropriate as clan relatives mentor each other and visit often. This team used a culturally-based survey recruitment procedure in another intervention study that yielded a 98% participation rate. We also anticipate a very high acceptance rate for this project due to multiple community members reaching out to [name] and asking to be involved in the study. Also, the tradition of having compassion, empathy, and respect for relatives and a 19-year history of working in the community will lead to successful recruitment and retention.

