- Since starting with the Báa nnilah program, what other support in addition to being in the program has made a difference for your health?
- In your observation, what changes have you noticed in the community as a result of this program?
- What do you see for yourself for the future?
 - What information/tips/techniques from the program will you use in the future?

- What ideas do you have for the future of the Ba nnilah program in the Crow community?

Aho. Thank you for your time today. You are helping us to make the Ba nnilah program most effective.

Facilitator measures of fidelity

1. Recruitment: Mentor will have a “Participant Notebook” where they keep track of names and contact information of community members they recruited, location of recruitment, and date of recruitment. We will also gather information on emergency contacts for each participant. We will use this notebook to track recruitment efforts. Note: The Participant Notebook will not be linked to the outcome data in order to protect confidentiality of participant information.
2. Entry into study: The Participant Notebook will also have information on the date the mentor consented the participant and the date they held a meeting with the participant to hear their health story.
3. Retention:
 - a. Each gathering will include a mentor check list of participant attendance, which the mentor will transfer into the Participant Notebook, which will be changed to number of gatherings attended by each participant in the database.
 - b. For gatherings missed by participants, the mentor will indicate if the participant provided a reason for missing the gathering
 - c. Participants who drop out of the study will be contacted by project staff (not the mentor who is leading their gatherings) and asked for their reasons for drop out.
4. Dose: Each gathering will include a mentor check list of which components of the gathering they facilitated and the length of the gathering in minutes. An example is included in the materials. The evaluation will consist of the number of manual-based intervention components delivered divided by the total number intended. The checklist also includes three questions:
 - a. How comfortable were you in leading this gathering?
Not at all comfortable to Very comfortable on a scale of 1-10
 - b. How confident were you in leading this gathering?
Not at all confident to Very confident on a scale of 1-10
 - c. Please share any comments you have about leading this gathering.

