- Gain knowledge and tools for healthy living and self-care to improve your quality of life.
- Learn from mentors and other program members
- Share and apply Crow cultural strengths to address ongoing health concerns.
- Learn about nutrition and physical and emotional health tools and exercises through hands-on activities.
- Gain support and help from program staff and other participants to apply what is learned to your self-care.

Messengers for Health will also host Baa nnilah community meetings to receive input and share our progress so we can better serve our Crow People.

Together let's take back our health!

Journey through the *Báa nnilah* Program

Our 10 mentors will each recruit 20 participants. Eligible participants have an ongoing illness and are 25 and older. Participants sign forms & identify family members and friends who want to be in a group together. By August 15, 2017.

Family members and friends who want to be together are randomly assigned to Fall (Nov 2017-Feb 2018) or Spring (April-July 2018) groups. There will be about 10 participants per group and 10 groups each in Fall and Spring.

Fall and Spring group participants come to orientation and fill out health surveys in local communities.
October 2017

10 Fall groups attend 7 *Báa nnilah* gatherings in local communities

Nov 2017-
Feb 2018

10 Spring groups stay in contact

Fall and Spring group participants fill out health surveys in local communities. March 2018

10 Fall groups stay in contact

April-July
2018

10 Spring groups attend 7 *Báa nnilah* gatherings in local communities

Fall and Spring group participants fill out health surveys in local communities. August 2018

Fall and Spring group participants fill out health surveys in local communities. December 2018

Báa nnilah information

- This program is for Crow men and women who have an ongoing illness.
- It is a partnership with MSU-Bozeman.
- There will be 7 gatherings in local communities - everyone will attend all 7 gatherings.
- Local mentors will lead the program.
- You will gain knowledge and tools for improving your health.
- You will learn from other members and use cultural strengths to address ongoing health concerns.
- There will be hands-on activities to learn about and apply physical activity, nutrition, and emotional health information.
- Members will support and help each other to apply what is learned to your every day life.
- Family members are welcomed to be involved.
- Meals will be served.

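### Grant text attached to the IRB application has the recruiting mentors assign participants, while the application, handout and SAP work with clusters; assignment precedes a self-reported baseline, and no concealment is described in the available text

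*Protocol*

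**What the plan says.** **Who assigns, and what unit.** In Protection of Human Subjects, under Recruitment and study orientation, the mentors lead recruitment, "will be trained to randomly assign participants to the intervention group or wait-list group using a permuted block randomization protocol", and "will recruit until they have 10 participants (each) in the intervention and wait-list group". No cluster is mentioned there. Section VII.A of the IRB application attaches this text as coming "from our grant application that contains human subjects information", and nothing available marks it as superseded. Under Facilitator measures of fidelity, item 2, the mentor's notebook records "the date the mentor consented the participant and the date they held a meeting with the participant to hear their health story".

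Section VII.B, item 1 of the application has people "randomly assigned by family/friend cluster to an intervention or wait-list control group". The participant handout (Journey through the program) agrees: "Family members and friends who want to be together are randomly assigned to Fall (Nov 2017-Feb 2018) or Spring (April-July 2018) groups". Neither says who performs the draw. The SAP places individuals within family/clan clusters, 45 in the intervention arm and 50 in the wait-list arm.

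**When.** The handout's first step is "Participants sign forms & identify family members and friends who want to be in a group together. By August 15, 2017". Assignment to Fall or Spring is the next step, followed by orientation and surveys in October 2017. Section VII.B gives the same order: consent, cluster assignment, baseline.

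**What happens at baseline.** The Data Gathering Meeting script (Measures) hands out the topics and dates of the seven gatherings and then introduces the tablet survey and the exercises. The primary outcome, the SF-12, is part of that survey.

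**The concern.** Two things are at stake.

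1. **Selection.** Followed as written, the attachment leaves allocation with the people who choose whom to approach, take consent and lead the sessions. It also uses a unit that neither the application nor the SAP uses. If such a person can foresee the next arm, the people enrolled can differ between arms in ways that adjustment for age, sex and number of illnesses need not capture.
2. **Baseline reporting.** Fall and Spring gatherings fall on different dates. A participant who has already been assigned and has just received gathering dates may know the arm when answering the SF-12. The baseline is the first point of each person's trend, so a shift in answers caused by that knowledge enters the SAP's test of whether change differed between groups.

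**Working it through.** The documents give no block size, standard deviation, correlation or size of shift, so there is no planned figure to reproduce. The steps below compare the texts and then illustrate the size of each risk.

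**1. The texts side by side**

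| Source | Assigned by | Unit | Order relative to baseline |
|---|---|---|---|
| Protection of Human Subjects attachment | Mentors | Participants | Not stated |
| IRB application VII.B | Not stated | Family/friend cluster | Before |
| Participant handout | Not stated | Family and friends together | Before |
| SAP | Not stated | Family/clan cluster (modelled) | Not stated |

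The SAP's counts give 104/45 = 2.31 and 107/50 = 2.14 people per cluster, so its cluster is not the individual.

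**2. Foreseeability, only if assignment was sequential**

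Assume individual assignment, past assignments known to the mentor, and a guess always placed on the arm with more places left. For a block of 2b, the expected share of correct guesses is [b + (4^b / C(2b,b) − 1)/2] / (2b).

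- Blocks of 2 (b = 1): [1 + (4/2 − 1)/2]/2 = 0.750.
- Blocks of 4 (b = 2): [2 + (16/6 − 1)/2]/4 = 0.708.
- One block of 20 (b = 10, the attachment's 10 + 10 places per mentor): [10 + (1,048,576/184,756 − 1)/2]/20 = 0.617.
- One batch draw after the list is closed: 0.500.

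**3. How a baseline shift carries into the contrasts**

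Inputs:
- Waves at weeks 0, 28, 54 and 78, assumed from the October 2017 baseline and the amended months (April/May 2018, October/November 2018, April 2019).
- The wait-list-only fifth wave from the last modification request, assumed at week 104.
- n = 104 and 107, from the SAP.
- SAP attendance indicator coded 0,1,1,1 (intervention) and 0,0,1,1 or 0,0,1,1,1 (wait-list).

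The model is generalised least squares with a random intercept and terms for group, weeks and group × weeks, with or without the indicator. Data are taken as complete; family clustering and the other covariates are left out.

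Hand check without the indicator, four waves: mean week = (0 + 28 + 54 + 78)/4 = 40. The sum of squares about it is 1600 + 144 + 196 + 1444 = 3384. A 1-point rise at week 0 changes that arm's slope by −40/3384 = −0.01182 per week. That is −0.92 over 78 weeks and −0.33 over 28 weeks.

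Effect of a 1-point upward baseline shift on intervention minus wait-list:

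| Shift in | Model | Waves | Week-78 contrast | Indicator coefficient | Wave-2 contrast |
|---|---|---|---|---|---|
| Intervention only | No indicator | 4 v 4 or 4 v 5 | −0.92 | – | −0.33 |
| Intervention only | Indicator | 4 v 4 | −1.08 | −0.57 | −0.96 |
| Intervention only | Indicator | 4 v 5 | −0.92 | −0.48 | −0.81 |
| Both arms equally | No indicator | 4 v 4 | 0.00 | – | 0.00 |
| Both arms equally | No indicator | 4 v 5 | −0.30 | – | −0.11 |
| Both arms equally | Indicator | 4 v 4 | −0.09 | −0.33 | −0.36 |
| Both arms equally | Indicator | 4 v 5 | −0.30 | −0.45 | −0.56 |

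The week-78 contrast is 78 × (group × weeks), because both arms have the indicator at 1 by then. The wave-2 contrast is 28 × (group × weeks) plus the indicator coefficient; for example −1.08 × 28/78 − 0.57 = −0.96. A shift in the wait-list arm only moves the week-78 contrast by 0.62 to 0.99 in the other direction. Results do not change for within-person correlations of 0.3, 0.5 or 0.7. Other wave timings (0/24/50/76 to 0/30/56/80, no indicator, four waves) give 0.88 to 0.94 at the last wave for the intervention-only case.

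**The case against.** **The attachment may simply be older.** It comes from the grant application, speaks of IRB review as still to come, and Aim 1 planned to refine the study protocol in Year 1. The application's own procedures, the handout and the SAP all use clusters. This makes it plausible that the mentor procedure was dropped. But the attachment was submitted as part of the current application, and nothing available states who replaced the mentors, so the need to reconcile stands.

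**Nothing states sequential assignment.** The handout's order (sign-up by mid-August, then assignment) fits one batch draw, and then foreseeability disappears. Staff, community meetings and tabling events also recruit, so mentors are not the only gatekeepers. The 62% to 75% range assumes individual assignment and does not describe a draw of 95 clusters. This objection largely stands: the range is an illustration of the attachment's procedure. No text says the draw was a batch either. The October 2017 modification request refers to about 190 people not yet consented or not yet seen at baseline, and its wording does not settle whether consent was complete by August.

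**Knowledge of the arm is inferred.** The script is generic, and the dates handout is not among the documents; it might list both seasons. For the baseline sessions, "The groups are based on the community in which they will attend the intervention meetings", which neither confirms nor excludes sessions held separately by arm. This stands: participants may have known, but the documents do not say that they did.

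**Safeguards exist.** There is a refusal log, a baseline comparison of outcomes by arm, and adjustment for age, sex and number of illnesses. These help. The comparison cannot separate chance imbalance from a reporting shift, and the covariates do not remove one.

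**Two stronger readings fail.** A reader might take the 104 and 107 participants, against 10 mentors × 10 = 100 per arm, as evidence that the stop-at-10 rule was not followed. The handout says about 10 per group, so ordinary overshoot explains them. A reader might also infer that allocation was in fact subverted; no document supports that.

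**Conclusion.** The contradiction over unit and operator is real, and so is the order of assignment before a self-reported baseline. Together they create a risk of selection and of a baseline reporting shift. Bias is not shown, and its size cannot be derived from the documents.

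- **Foreseeability** arises only under sequential assignment: 62% to 75% correct guesses for assumed blocks of 20 to 2 with individual assignment, 50% under one batch draw.
- **A shift in the intervention arm only** would carry about 0.9 to 1.1 of its size into the week-78 contrast. At wave 2, the only follow-up before the wait-list arm receives the program, it carries 0.33 without the attendance indicator and 0.81 to 0.96 with it.
- **An equal shift in both arms** might be expected to cancel. With the SAP's indicator in the model it does not: the indicator coefficient moves by −0.33 to −0.45.

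These fractions rest on assumed wave weeks, complete data and a simplified model. The absence of concealment is a statement about the available text only: some pages and the design figure are missing, and the Research Strategy tables cited in the attachment were not supplied. The point should be addressed; confidence is medium.

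**What to change.** **Plan wording.** Replace the attachment's assignment text. The project biostatistician or the MSU HELPS Lab generates and holds the sequence, and the family/friend cluster is the only unit. Mentors submit consented clusters, the list is closed, and all arms come from one batch draw. Arms are released, and gathering dates handed out, only after the baseline survey.

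The cost is a protocol edit, a reordered baseline session and one draw by people already on the project. Groups are finalised slightly later, which is tight with baseline planned for October and Fall gatherings from November.

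**Completed trial.** The draw cannot be redone, so the remedy is reporting:
- Reconcile the attachment with section VII.B, the handout and the SAP, including the family/friend and family/clan labels.
- State who generated, held and applied the allocation, its unit, whether it was one batch, and its timing relative to consent and baseline.
- Extend the SAP's baseline comparison by showing arm differences by mentor, with logged refusals by mentor.
- Set baseline arm differences in the self-reported measures beside those in the three performance tests, which are less exposed to knowledge of the arm.

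This costs a few descriptive tables and needs no new data.

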Participants will share their health stories with their *Aakbaabaaniilea* and with other members of their intervention group. In our preliminary study, we found that this was perceived by participants to be a beneficial experience. Participants in the *Baa niilah* intervention groups may receive benefits of learning from each other and from their Mentor on how to improve their chronic illness management. Our hope is that the proposed intervention will lead to improved management and that this intervention can be disseminated to other Native American communities in order to assist with chronic illness self-management strategies. The intervention methods are built upon strengths of the Apsáalooke culture and are culturally sensitive to ways of knowing and interacting. As a result of our culturally sensitive approach, the intervention meetings are likely to be a pleasurable experience for the participants.

Importance of the knowledge to be gained

Health statistics of Montana's Native American populations show significant health disparities that require effective interventions; however, intervention strategies with Native Americans that focus on chronic illness self- management are severely lacking. By adapting, testing, and disseminating an effective intervention that is based in the Apsáalooke Indian culture, there will be a reduction of negative consequences of chronic illness in this population, as well as meaningful information gained, which will inform other research and practices.

Data safety and monitoring plan (DSMP)

Using definitions and information in the June 10, 1998 NIH Policy for Data Safety and Monitoring, we consider this study to meet the criteria for a Phase III clinical trial as we are conducting an effectiveness trial where we are comparing a new treatment (*Baa niilah* intervention) to usual care and in which participants will be followed for 12-months post-intervention. This is a single-site study. We agree to work with the IC that will be funding this study regarding their roles and responsibilities listed in the policy, to include:

- Prepare or ensure the establishment of a plan for data and safety monitoring for all interventional

trials;

- Conduct or delegate ongoing monitoring of interventional trials;
- Ensure that monitoring is timely and effective and that those responsible for monitoring have the appropriate expertise to accomplish its mission;
- Oversee monitoring activities; and,

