group completing the survey approved by the IRB. We have one more data collection event and this event is only with the wait-list control group. We would like approval to add this question:

- What do you think is the best way to for us to learn what the Ba nnilah program did for its participants, family members, and for the Crow community as a whole?
 - If they say, “a survey” or “asking people who took part” say, “please explain” or “what questions would you ask?”

6. Have these requested changes been initiated?

No

Yes

7. How will the proposed modification(s) affect study participants?

Note: Federal regulations require IRB approval prior to changing a research procedure or deviating from IRB approved documents unless it is in the best interest of or for the safety of study participants.

This will not affect study participants except the minor changes to the interview protocol.

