Clinicaltrials.gov: Cover page

Official title of study:

Improving Chronic Illness Management With the Apsaalooke Nation: The Baa
Nnilah Project

NCT number: NCT03036189

Date of the document: 8/23/22

Statistical Analysis Plan

Statistical analysis. Statistical analyses were conducted using SAS 9.4®.³¹ Descriptive statistics were obtained for all study variables. Mean and standard deviation were calculated for continuous variables, and frequency and percentage for categorical variables. Distributions of continuous variables were examined for non-normality and outliers. Missing data patterns were examined for all variables. To compare the two study groups on baseline demographic characteristics and outcome measures, independent *t*-tests were conducted for the continuous variables, and chi-square tests for the categorical variables.

To test the main hypotheses regarding the effectiveness of the intervention and longitudinal trend on each outcome measure, a hierarchical linear modeling (HLM) approach was adopted, and each hypothesis was tested in SAS 9.4 using the *Proc Mixed* procedure. Observations were nested within individuals and individuals nested within family/clan clusters. Up to four observations (i.e., measurements over four waves of data collection) per participant in the intervention group ($n = 104$, number of clusters = 45) and up to five observations per participant in the WLC group ($n = 107$, number of clusters = 50) were obtained. All available observations were included in the analysis to test whether the outcome measure changed significantly over time (i.e., number of weeks since baseline) and whether the change significantly differed between the two study groups.) Time-invariant covariates included age at baseline, sex, study group membership, number of chronic illnesses, and number of gatherings attended. In addition, a dummy variable indicating whether each participant had attended intervention sessions at each time of data collection was included in the analytical model as a time-varying covariate. The number of valid data points varied across individuals, as well as by time and by variable within each individual, because participants could 1) miss a data collection but complete subsequent data collection(s) and/or 2) choose not to complete a physical test or a survey question. Full information maximum likelihood estimation (MLE) was used to handle missing data, which allowed us to use all available non-missing data.

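### The SAP model estimates no effect at 6 or 12 months after the programme, and its single attendance indicator is unbiased only if the effect stays constant

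*Protocol*

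**What the plan says.** Protocol, Aim 2, primary hypothesis: quality of life on the SF-12 will improve "compared to a wait-listed control group immediately following the intervention and at 6 and 12 months post-intervention". The secondary hypothesis uses the same three times. The Data safety and monitoring plan describes an effectiveness trial "in which participants will be followed for 12-months post-intervention".

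Protocol, Research Procedures: the wait-list arm goes through the sessions after the second data collection. A later IRB amendment puts the post-baseline surveys in April/May 2018, October/November 2018 and April 2019. The last amendment, made after four surveys, says "We have one more data collection event and this event is only with the wait-list control group".

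SAP, Statistical analysis:
- Data: "Up to four observations (i.e., measurements over four waves of data collection) per participant in the intervention group" (n = 104, 45 clusters) and "up to five observations per participant in the WLC group" (n = 107, 50 clusters).
- Stated tests: change over time ("i.e., number of weeks since baseline) and whether the change significantly differed between the two study groups").
- Fixed covariates: "Time-invariant covariates included age at baseline, sex, study group membership, number of chronic illnesses, and number of gatherings attended".
- Exposure, the one covariate that can change from survey to survey: "a dummy variable indicating whether each participant had attended intervention sessions at each time of data collection was included in the analytical model".

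The SAP gives no term for time since the sessions, no interaction with the attendance indicator and no contrast at 0, 6 or 12 months. It does not say which coefficient is the intervention effect.

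**The concern.** The hypotheses make three separate claims, and two of them concern durability. A single indicator that switches on after the sessions and stays on can return only one number, so the 6- and 12-month claims have nothing in the model that corresponds to them.

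That number is also not a plain average of the three effects. From the third survey both arms have had the programme, so participants treated earlier help to set the background trend against which newly treated participants are judged. A fading benefit in the first arm is then partly read as background decline and credited to the programme. A growing benefit is partly read as background improvement and deducted. At stake is a report of lasting benefit when none remains at 12 months, or of no benefit when one has built up slowly.

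**Working it through.** The documents give no effect size, SD, alpha or power figure, so there is no planned number to reproduce. The check computes what the model would return for known true effects.

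**Inputs**
- From the SAP: arms of 104 and 107; four and five surveys.
- From the IRB amendments: survey months, taken as weeks 0, 28, 54 and 78. The wait-list-only fifth survey has no date; week 104 is assumed.
- Assumed: outcome SD 1, within-person correlation 0.6, full attendance, no dropout, no family-cluster effect, no common time change, indicator equal to 1 at every survey after the sessions. Straight-line weeks and a group-by-weeks term are my reading of the SAP's wording.
- e0, e6, e12: true effects in SD just after, 6 months after and 12 months after the sessions.

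**Step 1: true arm differences (intervention minus wait-list)**

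D1 = 0; D2 = e0; D3 = e6 − e0; D4 = e12 − e6. Only D2 compares treated with untreated participants.

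**Step 2: survey-wave terms plus the indicator, by hand**

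Survey 5 has one arm only and is absorbed by its own wave term. The indicator differs between arms only at survey 2, so its coefficient is

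D2 − (D1 + D3 + D4)/3 = e0 − (e12 − e0)/3 = (4/3)e0 − (1/3)e12.

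- Fading 0.30/0.15/0: (4/3)(0.30) = 0.40.
- Growing 0/0.15/0.30: −(1/3)(0.30) = −0.10.

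The 12-month effect enters with a negative weight.

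**Step 3: the SAP as read (weeks, group, group by weeks, indicator)**

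Generalised least squares gives a coefficient of about 1.36·e0 + 0.33·e6 − 0.69·e12. With the third survey at week 53 the weights are 1.34, 0.34 and −0.68. The within-person correlation does not change the weights, only the standard error (0.08 at correlation 0.6).

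| True 0/6/12-month effect | Weeks model | Wave terms (Step 2) |
|---|---|---|
| 0.30/0.30/0.30 | 0.30 | 0.30 |
| 0.30/0.15/0 | 0.46 | 0.40 |
| 0.15/0.225/0.30 | 0.07 | 0.10 |
| 0.10/0.20/0.30 | about 0 | 0.03 |
| 0/0.15/0.30 | −0.16 | −0.10 |

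For example, 1.36(0.30) + 0.33(0.15) = 0.408 + 0.050 = 0.46, and 0.33(0.15) − 0.69(0.30) = 0.050 − 0.207 = −0.16. Adding group by weeks to the wave terms brings the fading result to 0.37. The −0.16 would be statistically significant about 49% of the time (41% to 61% for correlations 0.5 to 0.7).

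**Step 4: does the group-by-time test fill the gap?**

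No. For a constant benefit it is exactly 0. For the fading and growing paths in the second and last rows it is about −0.03 and +0.03 SD per 26 weeks, roughly 0.9 standard errors.

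**Step 5: three terms for time since the sessions, with arm and wave**

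Solving Step 1: e0 = D2 − D1; e6 = D3 + D2 − 2·D1; e12 = D4 + D3 + D2 − 3·D1. The true values return exactly in every row of the table.

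The variance of one arm difference, after the person effect cancels, is v = 0.4(1/104 + 1/107) = 0.00758. Then:
- e0: √(2v) = 0.12
- e6: √(6v) = 0.21
- e12: √(12v) = 0.30
- single indicator with wave terms: √(4v/3) = 0.10

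This model has 9 parameters for 9 arm-by-survey means. Adding group by time makes 10, which cannot be estimated. With straight-line weeks, group by time can stay.

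**The case against.** **The SAP never calls the indicator the treatment effect.** It lists it as a covariate, and the only group comparison that it words as a test is the difference in change. This stands. A reader might infer that the one coefficient would be reported as the effect at all three times, but the documents do not say so. It does not rescue the plan, because Step 4 shows that the group-by-time term does not test the hypotheses either.

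**A growing benefit need not look harmful.** A reader might infer that it generally does. The figures do not support that. For straight-line growth the sign turns only when the 12-month effect exceeds about 3 times the immediate one in the weeks model, or 4 times with wave terms. Every growing path tried was understated; reversal needs little immediate effect.

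**The indicator is not the only exposure term.** The number of gatherings attended is also in the model. True, but it is constant within a person and carries nothing about timing.

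**The model equation is not written out.** The indicator could mean 1 only at the first survey after the sessions. That reading sets the 6- and 12-month effects to zero, so it cannot test them either.

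**The limit lies in the design.** This is the strongest point, and it stands. After survey 2 nobody in the wait-list arm is untreated, so no model yields a randomised 6- or 12-month comparison. Step 5 recovers those effects only if both arms follow the same path. With a constant 0.30 in the first arm and 0.40 in the second, D2 = 0.30 and D3 = D4 = −0.10, and Step 5 returns 0.30/0.20/0.10, a fade that does not exist. Unequal effects are plausible, since the facilitator interview shows that mentors led a first and then a second group.

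**Conclusion.** The concern holds in this form: the 6- and 12-month parts of the primary and secondary hypotheses have no matching estimate in the SAP, and the attendance indicator is unbiased only for a constant effect. The missing estimates follow from the SAP's text and need no numerical assumption.

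The size of the bias depends on the assumed survey weeks, full attendance, the absence of clustering and dropout, and the true path. A fading effect was overstated in every specification tried (0.37 to 0.46 against an immediate effect of 0.30 and a 12-month effect of 0). A growing effect was understated, with null or reversed results only when little of it is immediate. The repair does not create a randomised test at 6 or 12 months; only the second-survey comparison has untreated controls.

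**What to change.** In the SAP, Statistical analysis:

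1. Replace the attendance indicator with a four-level factor for time since the participant's own session block: not yet, just after, about 6 months, about 12 months (intervention arm surveys 2, 3, 4; wait-list arm surveys 3, 4, 5).
2. Fit it with arm and survey wave and without group by time, or with straight-line weeks, where group by time may stay. State which.
3. Report three effects with confidence intervals.
4. Name the just-after effect, anchored on the second-survey comparison with untreated controls, as the confirmatory test.
5. Label the 6- and 12-month effects exploratory. State that they have no untreated comparator and assume the same effect path in both arms and, with wave terms, parallel background trends.

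**Cost.** No new data, only revised SAP wording and a refitted model. With wave terms, the group-by-time test is given up and the fifth survey adds nothing to the 12-month estimate. Standard errors rise to about 0.12, 0.21 and 0.30 SD before family clustering, against 0.08 to 0.10 for the single indicator. With weeks and group by time they are 0.14/0.22/0.32 at correlation 0.5 and 0.11/0.17/0.25 at 0.7. At a standard error of 0.30, a true 12-month effect of 0.30 SD has about 17% power and 80% power needs about 0.85 SD, so the 12-month result will probably be inconclusive.
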